In order to evaluate the range of genomic findings, we utilize a framework for “binning” genes into categorical lists that will facilitate informed decision-making. We will utilize the following categories of genomic results in this study:

1. ***Next-Generation Sequencing Newborn Screen (NGS-NBS):*** Medically actionable childhood conditions, representing the core results that will be returned to all participants in the study. The NGS-NBS includes genes implicated in conditions that are currently screened for in standard state newborn screens,

including metabolic disorders, endocrine disorders, and hearing loss. In addition, we will include other medically actionable conditions that are not amenable to current screening methods but can be detected using genetic sequencing (e.g. hereditary cancer susceptibility with onset or initiation of screening protocols in childhood). The criteria for determining which genes to include in the NGS-NBS are part of the overall aims of the research project (see below). These findings represent the default set of results that would be returned with every sequencing report. All parents consenting to sequencing of their child will learn if their child has one or more variants in this category that are determined to indicate with high likelihood that the child has or will likely develop a particular genetic disorder.

2. ***Additional genomic findings:*** Conditions that do not meet the threshold for inclusion in the NGS-NBS. Only parents randomized to the “decision” group will be asked to decide if they wish to learn any, all or none of these additional findings. Human curation and analysis of these variants will **not** be performed until parents request them. This analysis would **not** be done for children in the control group (see randomization procedure below). These additional findings fall into the following categories:

A. *Medically-actionable adult onset conditions:* These disorders would be similar to the kinds of results described in NGS-NBS (above) but are related to conditions in which the onset or initiation of screening protocols occurs in adulthood, such as Hereditary Breast and Ovarian Cancer gene mutations.

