4. Non-canonical splice site variants include those that occur within 3-10 nucleotides of the intron-exon border.

5. UTR variants are annotated as being located in the 5’ untranslated or 3’ untranslated regions of the mRNA.

6. MAF data will be derived from frequency data from the 1000 Genomes Project and ExAC; the highest of the minor allele frequencies for a given variant from any ethnic group will be used to evaluate the MAF threshold criteria.

Integral to the efficient diagnostic assessment of an entire genome or exome will be the establishment of *a priori* panels of genes to be assessed under certain clinical situations. One of the major tasks of the clinical and molecular teams will be the development of such lists relevant to the categories of disorders that are present in the Diagnosed Cohort. Once established, these lists will be used to query patients’ variant data to identify all variants in genes of possible diagnostic significance in the context of their medical presentation. A molecular analyst will evaluate the prioritized variant list and provide a preliminary interpretation of the case to the molecular sign-out committee.

The committee will make a final pathogenicity determination and decide whether any variants exceed our threshold for reporting (Table 2). Because of the presence of a phenotype in the individual being sequenced, results considered to be clinically relevant would include the “known pathogenic,” “likely pathogenic,” and “variant of uncertain significance” as determined by the molecular sign-out committee.

Table 2: Categories of findings deemed reportable for an indication-based analysis

Result Category	Variant types	Zygosity	Phenotype ⁸	Inheritance
Positive-Definitive	KP ¹	Heterozygous	Concordant	Dominant ⁹
	KP	Homozygous or compound heterozygous ⁶	Concordant	Recessive ¹⁰
Positive-Probable	LP ²	Heterozygous	Concordant	Dominant
	KP	Potentially compound heterozygous ⁷	Concordant	Recessive

	LP	Homozygous or potentially compound heterozygous	Concordant	Recessive
--	----	---	------------	-----------

Uncertain-VUS	VUS ³	Heterozygous	Concordant	Dominant
	VUS,	Homozygous	Concordant	Recessive
	VUS plus KP/LP ⁴	Compound heterozygous or potentially compound heterozygous		
Uncertain-AR het	KP/LP ⁵	Heterozygous	Concordant	Recessive
Uncertain-Contributory	Any	Any	Partially matching	Any

1. KP = Known Pathogenic

2. LP = Likely Pathogenic

3. VUS = Variant of Uncertain Clinical Significance

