In the “Well-Child” cohort there will be no phenotype to inform a diagnostic list. In addition, all conditions unrelated to the phenotype known for patients in the “Diagnosed Cohort” would be considered “incidental” to their primary indication for sequencing. Therefore, the analysis of the NGS-NBS list and additional genomic findings will be more akin to screening than diagnostic testing. In this setting, the prior probability that an individual has a rare Mendelian disorder will be very small (based on the population prevalence of the disorder), and thus the positive predictive value of genomic information will be strongly influenced by the specificity of the results. Both the “Diagnosed Cohort”

and “Well-Child Cohort” will receive results from the “NGS-NBS” gene list. In order to minimize false positives, we will use stringent criteria for return of results and will only return variants that are deemed to be “pathogenic” or “likely pathogenic” and consistent with the expected inheritance pattern of the condition (eg. homozygous or presumed compound heterozygous variants in the case of a recessive condition).

Variants will be computationally selected for their presence in a gene on the NGS-NBS list, their likely pathogenic significance and, in the case of recessive conditions, whether one or two mutations are present (34). Given the large number of possible genomic findings, and the low *a priori* likelihood that individuals in the “Well-Child” cohort would be affected with any given rare genetic disorder, it will be critical to strike a balance between the “sensitivity” and the “specificity” of the analysis so as to correctly identify individuals at high risk for a treatable genetic condition without overwhelming the molecular analysts, MGL, and clinicians with large numbers of variants of uncertain significance. This analysis will utilize the same computational classes as described in Table 1, with additional informatic filtering to determine which variants qualify for human review. We will review variants that satisfy the following conditions:

- 1) For genes associated with conditions inherited in a dominant fashion, we will review any variants in computational classes A and B;
- 2) For genes associated with conditions inherited in a recessive fashion, we will review variants in cases where two or more variants from computational classes A, B, or C are present.

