Cases fulfilling these criteria will undergo review by a molecular analyst and the molecular sign-out conference, and only variants determined to be “known pathogenic” or “likely pathogenic” and consistent with the expected inheritance pattern would be returned in the context of NGS-NBS. All other cases will be reported as “negative.” This approach is an inherently conservative one. We recognize that the strict thresholds outlined above will inherently have imperfect sensitivity for detecting clinically relevant variants, but at the same time this approach will have higher specificity and therefore protect against false positive results. This is also a pragmatic approach, since it will be impossible for a human to comprehensively review each of the many variants that will be identified in every individual. Thus, the balance we are striving to achieve is to maximize clinical sensitivity and specificity, while minimizing the effort required of a human molecular analyst.

CLIA Confirmation:

All results deemed reportable in the NC NEXUS study will be confirmed by orthogonal methods (Sanger sequencing) in the CLIA-certified UNC Hospitals MGL (Mol Gen Custom DNA Sequencing, see Appendix 7). A clinical report will be generated and approved by a board-certified molecular geneticist or pathologist. This result will be provided to the parents and will be eligible to be included in the electronic health record (NC NEXUS NGS-NBS Electronic Medical Record (EMR): Appendix 20 and NC NEXUS Additional Results Electronic Medical Record (EMR) Consent: Appendix 21).

Randomization:

After sequencing and analysis of the indication-based analyses and/or NGS-NBS are complete, the couple will be randomized into a “decision group” or a “control group”. The couple will be contacted to arrange a return of results visit with a geneticist and genetic counselor.

Randomization will be computer implemented using permuted block randomization with blocks of randomly varying size. Participants will be stratified for block randomization based on three parameters: study cohort (“Diagnosed Cohort” or “Well- child Cohort”), language preference (“English” or “Spanish”), and the relationship status of the parent(s) giving consent (“Single” or “Couple”). In this way, we will achieve optimum randomization within each of these groups.

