Diagnostic Findings: The return of results related to a known diagnosis is straightforward and non-controversial. Emotional distress is possible any time that parents learn their child has a genetic condition. However, parents participating in the “Diagnosed cohort” already know that their child has a disorder with a likely genetic etiology, and research indicates that risk is minimal when genetic information is relayed by a genetic counseling team in an appropriate setting.

NGS-NBS Findings: For parents of participants with positive NGS-NBS findings (not related to a known diagnosis), there is risk for an adverse psychological impact. We expect that the degree of anxiety and distress would be equivalent to that of parents whose child receives a positive standard newborn screen result. This psychological reaction is likely to be tempered by the medically actionable nature of the findings.

Additional genomic findings: For parents randomized to the “decision group” who choose to learn about carrier status in their child, we expect that the psychological impact will be minimal, and similar to that of parents who learn that their child is a carrier of Cystic Fibrosis or Sickle Cell anemia through the standard newborn screening program. For those who choose to learn additional diagnostic information about their child and subsequently receive unexpected information indicating their child has a genetic health risk, the magnitude of psychological distress is unpredictable and depends on the parent and the findings. However, the chance of such findings is very small.

Mitigation: The risks associated with parental responses to genetic information about their child are complex and form the basis of the need for this research project. We will provide genetic counseling and referral to specialists as needed for any positive results.

All study team members who have contact with study participants are already trained (physicians and genetic counselors) to recognize and probe indicators of possible distress (e.g., participants’ description or display of distress-related symptoms).

We will collect data on distress (depressive symptoms, anxiety) before return of results (to establish baseline levels) and after return of results, allowing us to examine changes in distress over time.

The decision aid is being designed to help families understand the risks and benefits of study participation and make an informed choice based on their values and preferences.

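### In the NGS-NBS screen, a listed pathogenic recessive variant above 5% in any one reference group cannot trigger review; whether one exists on the gene list needs a query

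*Combined protocol and SAP*

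**What the plan says.** Table 1, under Indication-based analysis, sorts variants into classes A to H. Class A needs a listing (disease mutation in HGMD, or pathogenic or likely pathogenic in ClinVar) and a minor allele frequency (MAF) below 5%. Class H takes any variant above 5%, and database status plays no part in it. Note 6 names 1000 Genomes and ExAC as the frequency sources and fixes which frequency is tested: "the highest of the minor allele frequencies for a given variant from any ethnic group will be used to evaluate the MAF threshold criteria".

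The section NGS-NBS and Additional Genomic Findings carries this over to the screen: "This analysis will utilize the same computational classes as described in Table 1", with further filtering on top. For recessive genes, "we will review variants in cases where two or more variants from computational classes A, B, or C are present". Cases that meet the criteria go to an analyst and the sign-out conference. For the rest, "All other cases will be reported as" negative. The same paragraph concedes that "the strict thresholds outlined above will inherently have imperfect sensitivity for detecting clinically relevant variants".

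On content, Categorization of possible genomic information states: "The NGS-NBS includes genes implicated in conditions that are currently screened for in standard state newborn screens". I found no exemption from the 5% ceiling for listed variants.

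**The concern.** The ceiling is tested against the maximum over groups, and the class then decides whether a person looks at the case at all. A variant that is common in one group and rare elsewhere is therefore removed for every child screened, on frequency alone, even if both databases list it as pathogenic. A recessive disease allele that is common in one population is where this could happen.

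Two things would be at stake. The first is a negative screen report for an affected child. The second is the filter itself: the protocol's Revised results section treats the criteria for analysing and reporting variants in NGS-NBS as a core research question, and a gap that depends on ancestry would be built into those criteria unseen.

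**Working it through.** The plan states no figure on this point, so there is none to reproduce. The check applies the written rule, then sizes the effect over an assumed range.

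**Inputs from the protocol**
- Class A below 5%, class H above 5% (Table 1); the highest group frequency is the one tested (note 6).
- Recessive trigger: two or more variants from classes A, B or C; otherwise negative (NGS-NBS and Additional Genomic Findings).
- 200 Well-Child infants (Study Design).
- Equal thirds Black, White and Hispanic (Sample size determination). This is an assumption made there for a power calculation on mothers. Applied to Well-Child infants it gives 200 / 3 ≈ 67 per group.

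**Assumed, not in the documents**
- MAF q of the variant in one group, zero in the other two.
- Hardy-Weinberg proportions.
- A homozygous variant counts as two toward the trigger.

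**Step 1: the class.** For a listed variant, q = 4.9% gives class A and counts toward review. At q = 5.1%, 6%, 8%, 10% or 12% it is class H and does not count.

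**Step 2: who is lost.** A homozygote has no countable variant. A child with the class H variant and one class A, B or C variant has only one. Neither meets the trigger, so both are negative. A child who happens to have two other class A, B or C variants in the gene is still reviewed.

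**Step 3: frequency of homozygotes.** Frequency = q²; expected number = 67q²; chance of at least one = 1 − (1 − q²)^67.

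| Assumed q | Homozygotes | Expected among 67 | Chance of at least one |
|---|---|---|---|
| 5.1% | 1 in 384 | 0.17 | 16% |
| 8% | 1 in 156 | 0.43 | 35% |
| 10% | 1 in 100 | 0.67 | 49% |

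**Step 4: share of affected children in that group not selected.** Let all other class A to C disease alleles in the gene total r. Affected children occur at (q + r)², and only those with two other alleles (r²) are reviewed. The share lost is 1 − r² / (q + r)².
- q = 5.1%, r = 1%: 1 − 0.0001 / 0.003721 = 97.3%. With r = 0.1% it is 99.96%.
- q = 10%, r = 1%: 1 − 0.0001 / 0.0121 = 99.2%. With r = 0.1% it is 99.99%.

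**Step 5: the part played by the maximum rule.** Averaged over three equal groups, the same variant at 5.1%, 8% or 10% in one of them would have MAF 1.7%, 2.7% or 3.3% and stay in class A. In this range it is the use of the highest group, together with the ceiling, that moves it to class H.

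**The case against.** **No affected variant is shown.** This is the strongest objection, and it stands. The documents give no allele frequencies. The Risk Analysis mentions "Cystic Fibrosis or Sickle Cell anemia through the standard newborn screening program", but only to compare how parents react to carrier results. A reader might infer that a named condition on the newborn screen is certain to be missed. The documents may support the presence of such a gene on the list, but not a single allele above 5%. Such an allele alone implies homozygotes more often than 1 in 400 in its group, so few conditions could qualify. Conditions caused by many alleles, each below 5%, are untouched.

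**The ceiling is deliberate.** A reader might also infer that class A was meant to send every listed mutation to review. It was not: Table 1 makes a frequency below 5% part of the definition, and the same section warns that many listed variants have later been questioned. The plan openly accepts imperfect sensitivity in return for specificity. That acceptance is general, however. It mentions neither frequency alone barring a listed variant from human review nor the dependence on ancestry. The plan's stated answer to doubtful listings is manual review, which class H variants in the screen do not get.

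**The sensitivity outcome is safe.** It might seem that the primary sensitivity outcome is biased. That outcome is measured in the Diagnosed Cohort, whose indication-based analysis reviews all variants in phenotype-related genes and uses the classes only to set priorities. A diagnosed child's own condition is therefore unaffected. Only the screen is at issue: the Well-Child Cohort, and findings unrelated to the diagnosis in the Diagnosed Cohort.

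**There are safety nets.** The False negative results paragraph says that standard newborn screening continues for all participants. Indication-based reanalysis is offered if symptoms arise, and algorithm updates lead to reanalysis of earlier participants. These limit clinical harm. They do not correct the initial screen result or, unless someone looks for it, the filter.

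**Conclusion.** The gap follows directly from the text, but it is conditional. If an NGS-NBS gene has a listed pathogenic recessive variant above 5% in any one reference group, the screen cannot select a child of any ancestry for review on the strength of that variant. In the group where it is common, at least 97% of affected children would go unreviewed under the ranges assumed above. The expected count in this study is small: 0.17 to 0.67 homozygotes among about 67 Well-Child infants for q from 5.1% to 10%. This rests on assumed frequencies, Hardy-Weinberg proportions and equal thirds. Variants below 5% are not lost.

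The documents do not show that any child will in fact be missed, or that the most frequent screened conditions are lost as a class. The point is an unexamined hole in the filter that a single query would confirm or rule out.

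**What to change.** Keep the 5% ceiling and add an exception list. For each version of the NGS-NBS gene list:

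1. Query its genes once for variants listed as disease mutation in HGMD, or as pathogenic or likely pathogenic in ClinVar, whose MAF exceeds 5% in any group.
2. Have the molecular sign-out committee rule once on each and record the ruling in the variant database, which already stores interpretations for reuse.
3. Treat the variants it confirms as class A for the recessive review trigger, and say so in a note to Table 1.

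Removing the ceiling altogether is less attractive: every common mislabelled variant would then count toward the trigger, adding the review load that the plan tries to limit.

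The cost is a one-time curation of whatever the query returns; the documents do not show how many variants that is. If the filter changes, the protocol already requires a 5-day notice to the FDA and reanalysis of participants analysed under the previous version, so the query is cheaper early. If it returns nothing, the sponsor has documented that the ceiling does no harm for that gene list.
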